### 8.2 Specific Methods for Efficacy Analyses

All Efficacy Data are summarized by descriptive statistics as described in section 8.1.

#### 8.2.1 Statistical/Analytical Issues

##### 8.2.1.1 Adjustments for Covariates

Not applicable.

##### 8.2.1.2 Handling of Dropouts or Missing Data

Dropouts are not replaced.

Missing data are handled as described in section 7.

##### 8.2.1.3 Blind Review

Not applicable since this is an open label study.

##### 8.2.1.4 Multicentre Studies

This study is performed in Australia, Belgium, Germany, India, Italy, Norway, Poland, Spain, Tunisia, the UK and the US. Analyses are performed over all centres.

##### 8.2.1.5 Multiple Comparisons/Multiplicity

Not applicable.

### 8.3 Specific Methods for Safety Analyses

All Safety Data are summarized by descriptive statistics as described in section 8.1.

### 8.4 Specific Methods for Pharmacokinetic Analyses

Not applicable.

### 8.5 Specific Methods for Pharmacodynamic Analyses

Not applicable.

## 8.6 Specific Methods for Pharmacoeconomic Analyses

Not applicable.

## 9. Interim analyses

An analysis will be produced to support the New Drug Application Submission. This is comprised of two parts: a Briefing Book submission and then the NDA submission.

As this study is open label and there are no hypothesis tests, no consideration is required for masking or Type I error control.

The outputs to be presented as part of the Briefing Book and NDA analysis are outlined in a separate document. For both analysis the subgroup of treatment gap outlined in Section 7.1 is not required.

## 10. Overview of Tables, Listings and Figures

Unless otherwise stated summary tables are produced based on the complete analysis set mention in the respective section. The treatment groups from the ATTeST study are presented on all outputs.

### 10.1 Disposition of Patients

A listing presents study completion data, including the primary reason for study discontinuation, for the Total Set (TOT).

A table summarizes the disposition of patients in the Total Set. This includes a summary of the number of patients who completed the study, the number of patients who had a treatment interruption due to COVID-19, the number of patients who discontinued the study, and the primary reason for discontinuation.

The number of patients who attended Scheduled Visits is summarized (Visit Attendance) by absolute counts (n) and percentages (%) for the SAF.

### 10.2 Protocol Deviations

A listing presents all protocol deviation data as recorded in the course of the study.

#### 10.2.1 Inclusion and Exclusion Criteria

Listings present all patients who failed to meet at least one of the Inclusion or Exclusion criteria, along with all the failing Inclusion and Exclusion responses for the TOT.

### 10.3 Data Sets Analysed

The number of patients in each Analysis Set defined in Section 6.1 is summarized by absolute counts (n) and percentages (%) for the TOT. Percentages are based on the TOT.

A listing presents the inclusion into each Analysis Set, including the primary reason for exclusion from the FAS for the TOT.

### 10.4 Demographic and Other Baseline Characteristics

#### 10.4.1 Demographic Characteristics

A listing presents all demographic data for the SAF.

A table summarizes all demographic data, and additionally height, weight and BMI at baseline by summary statistics and absolute counts (n) and percentages (%) for the SAF.

#### 10.4.2 Medical History

The medical history data are listed as recorded in the CRF together with the MedDRA SOC and PT.

The number and percentage of patients reporting any medical history and any medical history for each system organ class and preferred term are summarized. Patients are summarized only once at any level (any history, system organ class, and preferred term) if they have multiple reports at the level. Data are presented for the SAF.

#### 10.4.3 Concomitant Medications, Therapies and Procedures

All prior and concomitant medications are listed, including verbatim descriptions and coded terms.

Prior medications, concomitant medications are summarized using the number and percentage of patients reporting any medication use, and the number and percentage of patients reporting each ATC drug class and generic drug name (WHO-DD preferred term). For each patient, multiple records of the same medication are counted once within a drug class and generic drug name.

Prior and concomitant medications are presented for the SAF.

All Non-drug Therapies and Procedures are listed, including verbatim descriptions and coded terms.

## 10.5 Exposure to Study Medication

A listing presents all Exposure to Study Medication data for the SAF (including overall duration, total number of completed infusions and data on each individual infusion).

Exposure to Study Medication data, including number of infusions received and duration of treatment are summarized by summary statistics for the SAF. The dexamethasone concentration data at each visit is summarized separately for the SAF.

## 10.6 Efficacy Results

### 10.6.1 Efficacy Analysis

#### (m)ICARS and RmICARS

The individual items of the ICARS are listed as well as the Full ICARS score, the “Modified” ICARS score, The Rescored “Modified” ICARS scores, and their respective changes from OLE-IEDAT baseline and ATTeST baseline. The listing is produced based on the SAF.

The modified ICARS score at baseline and each relevant follow-up visit (every 6 months), and the absolute change from OLE-IEDAT baseline and from ATTeST baseline to each relevant follow-up visit are summarized using summary statistics appropriate for continuous data as described in section 8.1.

The modified ICARS score at baseline and each 6-month interval from initiation of active treatment, and the absolute change from OLE-IEDAT baseline and from ATTeST baseline to each relevant 6 month interval are summarized using summary statistics appropriate for continuous data as described in section 8.1.

The Rescored modified ICARS scores at baseline and each relevant follow-up visit (every 6 months), and the absolute change from OLE-IEDAT baseline and from ATTeST baseline to each relevant follow-up visit are summarized using summary statistics appropriate for continuous data as described in section 8.1. Each scoring method is summarized separately.

The Rescored modified ICARS scores at baseline and each 6-month interval from initiation of active treatment, and the absolute change from OLE-IEDAT baseline and from ATTeST baseline to each relevant 6 month interval are summarized using summary statistics appropriate for continuous data as described in section 8.1. Each scoring method is summarized separately.

The full ICARS score at baseline and each relevant follow-up visit, and the absolute change from baseline to each relevant follow-up visit are summarized using summary statistics appropriate for continuous data as described in section 8.1.

The above summaries are presented for the FAS and repeated for the subgroups Age (<10 years, ≥10 years) and Region (India; Europe, Australia, Tunisia; United States).

For the FAS, the mean mICARS and Rescored mICARS (both methods) scores are plotted separately over time with a trend line. These plots are repeated displaying only patients in the EDS-EP High Dose treatment group from ATTeST.

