### Date of First Infusion of Active Treatment

The Date of First Infusion of Active Treatment is defined as the earliest infusion of active study drug, including infusions from the ATTeST study. For patients in the Non-Switch Placebo group

this will equal the date of first OLE-IEDAT Infusion. For all other patients this date will be received by CROMSOURCE in ADaM datasets from ATTeST.

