### Intervals from First Infusion of Active Treatment

Efficacy analysis outlined in Section 7.4.7 is displayed in 6-month intervals from first dose of active study drug, using data from the ATTeST Study.

These are derived by calculating day since First Infusion of Active Treatment:

$$\text{Day since First Infusion of Active Treatment} = (\text{Date of visit} - \text{Date of First Infusion of Active Treatment})$$

This is then mapped to 6 months intervals as follows:

| Interval  | Window            |
|-----------|-------------------|
| 6 months  | Day in [91, 273]  |
| 12 months | Day in [274, 456] |
| 18 months | Day in [457, 638] |
| 24 months | Day in [639, 821] |
| ...       | ...               |

Any day since First Infusion of Active Treatment < 91 will not be mapped to a 6-month interval.

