## OLE-IEDAT Baseline

*Final evaluations for the IEDAT-02-2015 trial will serve as baseline evaluations for patients continuing in the IEDAT-03-2018 study. The following “baseline” assessments for IEDAT-03-2018 will be done as part of the final Visit 15 evaluation in Study IEDAT-02-2015: physical/neurological examination; 12-lead standard ECG; laboratory evaluations [including hematology, clinical chemistry, urinalysis, serum pregnancy test (women of childbearing potential); special laboratory tests: HbA1c, CD4+ lymphocytes count and CRP]; assessment of physical development, sexual maturation, and the effect of treatment with dexamethasone on these aspects (Tanner scale); ICARS; CGI-S; CGI-S; EQ-5D-5L; C-SSRS; BMD; review of AEs and concomitant medications.*

If values are missing at the baseline visit, and the data are also recorded at screening, then the screening value are used in the summaries and calculations of change from baseline. Otherwise, the baseline value is missing for safety and efficacy endpoints.

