#### ICARS

*The ICARS is a 100-point, semi-quantitative scale offering a compartmentalized quantification of the following 4 sub-scores: Posture and Gait Disturbances (34 points), Kinetic Functions (52 points), Speech Disorders (8 points), and Oculomotor Disorders (6 points). (Trouillas, et al., 1997)*

*To maximize the consistency of the data obtained from the ICARS, the same site’s neurologist, qualified, trained, and certified in the use of the ICARS and with expertise in the field of AT disorders, will evaluate the same patient at approximately the same time throughout the study. ICARS ratings should be completed without consulting scores from the previous visit.*

*The primary efficacy endpoint is based on the Modified International Cooperative Ataxia Rating Scale (mICARS) score. This modified ICARS excludes items 17-19 related to oculomotor function, and Items 8-12 related to kinetic functions from the full 100-point ICARS.*

The modified ICARS is rescored, collapsing categories within specific items. This method results in a smaller total sum score across the ICARS domains. This is referred to as Rescored mICARS, to prevent confusion with modified ICARS. The rescoring method is outlined in Appendix 2 (Section 13.2) of this SAP. The ICARS is collected on the ICARS eCRF page. For the purpose of analysis, the total scores will be derived. If any of the individual ICARS scores contributing to the total score of interest are missing, then the total score will be set to missing.

The endpoints are the change of the mICARS and RmICARS scores from baseline to Visit 7 (6 Months) and all subsequent measures in 6-month intervals. These endpoints are repeated for all 6-month intervals since start of active treatment as outlined in Section 7.1.

The change in the full ICARS, which is the validated scale and the preference of European Regulators, from baseline to Visit 13 is presented as a sensitivity analysis.

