#### **Modified ICARS score - absolute change from OLE-IEDAT baseline**

For any follow-up visit (FU) the absolute change from OLE-IEDAT baseline is calculated as:

- mICARS absolute change from OLE-IEDAT baseline = mICARS score at FU  
- mICARS score at OLE-IEDAT baseline.

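### In the mICARS and RmICARS tables by time from first active drug, nothing limits change from OLE-IEDAT baseline to ratings made after that baseline, so some cells can be reversed in direction or zero by construction

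*SAP*

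**What the plan says.** SAP 7.1 (Intervals from First Infusion of Active Treatment) states that efficacy analysis "is displayed in 6-month intervals from first dose of active study drug, using data from the ATTeST Study". Time zero is "defined as the earliest infusion of active study drug, including infusions from the ATTeST study"; for the Non-switch Placebo group "this will equal the date of first OLE-IEDAT Infusion". The windows are days 91-273 (6 months), 274-456 (12 months), 457-638 (18 months) and 639-821 (24 months). The only stated exclusion is a day below 91.

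SAP 7.4.7 (ICARS) defines the endpoints as change in mICARS and RmICARS from baseline to Visit 7 and later six-monthly measures, then adds: "These endpoints are repeated for all 6-month intervals since start of active treatment as outlined in Section 7.1". The formula is "mICARS absolute change from OLE-IEDAT baseline = mICARS score at FU", less the score at OLE-IEDAT baseline.

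On the baseline itself, SAP 7.1 (OLE-IEDAT Baseline) says: "Final evaluations for the IEDAT-02-2015 trial will serve as baseline evaluations for patients continuing in the IEDAT-03-2018 study". Protocol 11.4.2 dates this to Visit 15/Month 12 of IEDAT-02-2015.

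SAP 10.6.1 then requires, for mICARS and again for RmICARS, the score at each interval from initiation of active treatment "and the absolute change from OLE-IEDAT baseline and from ATTeST baseline to each relevant 6 month interval". These are Tables 14.2-1.7 to 1.12 and 14.2-2.7 to 2.12.

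**The concern.** The rows of these tables run on one clock (first active drug) and the change is measured from a point on another (entry to the extension). For patients randomised to EDS-EP in ATTeST, the first clock starts about a year before the second. Their early rows therefore sit before or at the OLE baseline, and a change from that baseline is not a follow-up change there.

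Higher mICARS scores are worse (SAP 7.4.7), and Protocol 7.3 describes the disease as progressive. A patient who worsens between ATTeST Months 6 and 12 would appear with a negative change, which reads as improvement after 6 months of active drug, followed by exactly no change at 12 months. SAP 6.3 and section 10 place the seven ATTeST groups side by side on every output, so a single row would carry different meanings in adjacent columns. SAP 7.4.7 ranks mICARS as the most important secondary efficacy endpoint.

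**Working it through.** **Windows.** The lower edges are 3, 9, 15, 21 and 27 months at 365.25/12 days each: 91.3, 273.9, 456.6, 639.2 and 821.8. Rounded, these are 91, 274, 457, 639 and 822, which reproduces the four stated windows exactly.

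**Inputs.** Active drug starts at ATTeST Month 0 for the EDS-EP groups. It starts at about Month 6 for Visit 9 switchers, about Month 9 for Visit 12 switchers, and at the first OLE infusion for Non-switch Placebo (Protocol 7.1.3.4; SAP 6.3 and 7.1). ATTeST has an endpoint assessment at Visit 9, about Month 6, and a final one at Visit 15/Month 12. The ATTeST visit calendar is not in the documents, so the spacing is assumed: 21, 28, 30.4 (365.25/12) or 38 days per month. The outer values are the OLE infusion limits.

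**Mapping.** Day = (months since first active infusion) x spacing. Each cell shows day -> row.

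| Spacing (days) | EDS-EP throughout, ATTeST Month 6 | EDS-EP throughout, Visit 15 | Visit 9 switch, Visit 15 | Visit 12 switch, Visit 15 | Non-switch Placebo, OLE Month 6 |
|---|---|---|---|---|---|
| 21 | 126 -> 6 | 252 -> 6 | 126 -> 6 | 63 -> none | 126 -> 6 |
| 28 | 168 -> 6 | 336 -> 12 | 168 -> 6 | 84 -> none | 168 -> 6 |
| 30.4 | 183 -> 6 | 365 -> 12 | 183 -> 6 | 91 -> 6 | 183 -> 6 |
| 38 | 228 -> 6 | 456 -> 12 | 228 -> 6 | 114 -> 6 | 228 -> 6 |

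At 28 to 38 days, EDS-EP-throughout patients have the Month 6 rating in the 6-month row and the OLE baseline rating itself in the 12-month row. At 21 days both ratings fall in the 6-month row. For Visit 9 switchers the baseline rating falls in the 6-month row at every spacing; for Visit 12 switchers it does so only at 30.4 and 38 days. For Non-switch Placebo, Visit 15 is at day 0 or earlier and is not mapped.

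**What the column would read.** Suppose steady worsening of p points per 6 months, no treatment effect, 28-day spacing, no gap before the OLE, and both ATTeST ratings mapped. With score s at ATTeST baseline, EDS-EP throughout at 6 months is (s + p) - (s + 2p) = -p, and at 12 months (s + 2p) - (s + 2p) = 0.

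| Row | EDS-EP throughout | Visit 9 switch | Visit 12 switch | Non-switch Placebo |
|---|---|---|---|---|
| 6 months | -p | 0 | +p | +p |
| 12 months | 0 | +p | +2p | +2p |

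For EDS-EP throughout, change from ATTeST baseline in the same rows is +p and +2p. With assumed worsening of 1, 2 or 4 points a year, p is 0.5, 1 or 2. The 6-month cell then reads -0.5, -1 or -2, where change from ATTeST baseline is +0.5, +1 or +2.

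**The case against.** The strongest reply is that the SAP may never intend these cells to be filled. SAP 5.1 lists treatment subgroups and ATTeST baseline values as the content of the ATTeST datasets, and no section names post-baseline ATTeST ICARS ratings. The reference to ATTeST data in SAP 7.1 could mean only the date of first active infusion. The endpoint sentence in 7.4.7 begins at Visit 7, the change is defined for follow-up visits, and 10.6.1 attaches the word *relevant* to the intervals for changes but not to those for scores.

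Much of this stands. If no ATTeST follow-up ratings are loaded, the reversed 6-month cell is empty. If the Visit 15 rating is treated only as baseline, the zeros do not appear either. But *relevant* is undefined for intervals, 7.4.7 says the endpoints are repeated for all of them, and the only written exclusion is a day below 91. The Visit 15 rating has to be in the data as the OLE baseline, and nothing keeps it out of the mapping. Two programmers working independently from this text could reasonably produce different tables.

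A reader might go further and infer a pooled effect. Using ATTeST allocation shares (2/3 EDS-EP, 1/9 for each placebo subgroup), the 6-month row above would average 2/3(-p) + 1/9(0) + 1/9(p) + 1/9(p) = -0.44p. The documents do not support that figure: the SAP specifies no pooled column for these tables, and the group mix of patients entering the extension is not given.

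**Conclusion.** The point holds as a gap in the derivation rule. As written, SAP 7.1, 7.4.7 and 10.6.1 allow change from OLE baseline to be computed for ratings that precede that baseline or are that baseline. It would be too strong to say that the SAP prescribes a reversed change; each consequence depends on what is mapped.

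- If ATTeST post-baseline ratings are mapped, the 6-month cell for EDS-EP throughout is an earlier score minus a later one, and worsening shows as improvement.
- If the Visit 15 rating is mapped, the 12-month cell for that group and the 6-month cell for Visit 9 switchers are 0 by construction. Patients whose OLE baseline is the OLE screening value, after COVID-19 discontinuation, need not show an exact zero.
- In either case the 6-month cell for Non-switch Placebo is a genuine forward change, so the columns are not comparable.

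The row placement rests on the assumed spacing and is the same at 28, 30.4 and 38 days for these groups; at 21 days the EDS-EP-throughout zero moves to the 6-month row. The size in points depends on the rate of progression, which the documents do not give. The damage is confined to one statistic in twelve descriptive tables. Actual scores, change from ATTeST baseline and the by-visit tables are unaffected, and no error rate is involved. The change should be made because the affected scale is the leading efficacy measure and the error would be in the direction of change.

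**What to change.** In SAP 10.6.1, for the tables by time from initiation of active treatment, derive change from OLE-IEDAT baseline only for ratings dated after the OLE baseline assessment and leave it blank otherwise. Show ratings on or before the OLE baseline only as actual values and as change from ATTeST baseline. In SAP 5.1 and 7.1, state which ATTeST ratings are supplied and mapped to the intervals.

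At 28-day spacing, the first filled row for EDS-EP throughout would then be 18 months: OLE Month 6 falls on day 504, 532 or 580 for a gap of 0, 28 or 76 days between Visit 15 and the first OLE infusion. OLE Month 12 (days 672 to 748) fills the 24-month row.

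The cost is a few sentences in the SAP and one condition in the ADaM derivation. No new data are needed.

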#### *Handling of Dropouts and Missing Data*

Patients who discontinue treatment prematurely, i.e. prior to the Month 12 visit, are defined as dropouts. All final Month 12 (Visit 13) evaluations should be performed at the time of discontinuation.

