### 6.3 Subgroup Definitions

Patients are grouped by their treatment group in the ATTeST study: EDS-EP Low Dose, EDS-EP High Dose, Non-switch Placebo, Visit 9 Low Dose, Visit 9 High Dose, Visit 12 EDS-EP Low Dose, and Visit 12 High Dose. All outputs contain columns to display these groups.

The following endpoints are also summarised by subgroups for Age (<10; ≥10 years) and Region (India; Europe, Australia, and Tunisia; United States):

- ICARS
- mICARS
- RmICARS
- CGI-C
- CGI-S
- EQ-5D-5L

Patients with a treatment gap of greater than 76 days between the ATTeST study and the OLE-IEDAT study are presented as a separate subgroup for outputs as outlined in Section 10.

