### Duration of treatment

Duration of treatment on OLE-IEDAT study is derived as:

- Date of Last Infusion – Date of First OLE-IEDAT Infusion + 1.

The overall duration of active treatment from ATTeST baseline is derived as:

- Date of Last Infusion – Date of First Infusion of Active Treatment + 1.

For a definition of Date of first/last OLE-IEDAT infusion and date of first infusion of active treatment, see section 7.1.

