### 7.4.7 Efficacy Variables

The “Modified” International Cooperative Ataxia Rating Scale (mICARS) is the most important of the secondary efficacy endpoints.

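### In the mICARS and RmICARS tables indexed by time from first active infusion, neither planned change column starts at first active drug for the four Visit 9 and Visit 12 switch groups

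*SAP*

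**What the plan says.** SAP 7.1 sets the clock: "The Date of First Infusion of Active Treatment is defined as the earliest infusion of active study drug, including infusions from the ATTeST study". On that clock, efficacy "is displayed in 6-month intervals from first dose of active study drug, using data from the ATTeST Study". The printed windows are days 91–273 (6 months), 274–456 (12), 457–638 (18) and 639–821 (24), and the pattern continues. Days below 91 are not mapped.

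SAP 7.4.7 defines mICARS and RmICARS change from OLE-IEDAT baseline and from ATTeST baseline only. It then adds: "These endpoints are repeated for all 6-month intervals since start of active treatment as outlined in Section 7.1". SAP 10.6.1 carries the same two anchors into the interval tables: "the absolute change from OLE-IEDAT baseline and from ATTeST baseline to each relevant 6 month interval are summarized".

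SAP 6.3 shows seven ATTeST groups on every output. Besides EDS-EP Low Dose, EDS-EP High Dose and Non-switch Placebo, these are "Visit 9 Low Dose, Visit 9 High Dose, Visit 12 EDS-EP Low Dose, and Visit 12 High Dose". SAP 7.4.7 says that mICARS "is the most important of the secondary efficacy endpoints".

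For exposure, the SAP does use the active-treatment clock. Under the phrase "The overall duration of active treatment from ATTeST baseline is derived as", SAP 7.4.6 subtracts the date of first active infusion from the date of last infusion and adds one day.

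**The concern.** The only purpose of the interval tables is to line patients up by time on drug. A reader of a 12-month row will take the change beside it as change over 12 months of treatment. For the switch groups, no column gives that quantity. One column mixes in placebo time and the other starts after treatment has already begun. Exposure and change therefore run on different clocks for the same patients.

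The window rule has a second, smaller gap. It assigns ratings by day but does not say which one counts when two scheduled ratings fall in one window. The SAP's other rules go by nominal visit label. They settle which record represents a visit, but they cannot choose between two visits with different labels. Two programmers could produce different counts and means from the same text.

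**Working it through.** **Windows.** The printed upper bounds follow floor(365/12 × (6k + 3)):
- k = 1: 273.75 → 273
- k = 2: 456.25 → 456
- k = 3: 638.75 → 638
- k = 4: 821.25 → 821

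All four match SAP 7.1, so the rows are calendar-day windows.

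**Timing inputs (nominal, ATTeST completers).** Protocol 7.1.3.4 puts the two placebo switches inside ATTeST at about 6 and about 9 months. OLE-IEDAT baseline is the final ATTeST evaluation, Visit 15/Month 12 (SAP 7.1; Protocol 11.4.2). Matching Visit 12 to the 9-month switch is an inference from the visit numbering.

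**Offset of each baseline from first active drug.**

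| Group | Active start, months after ATTeST baseline | Placebo time in change from ATTeST baseline | Time on drug left out of change from OLE baseline |
|---|---|---|---|
| EDS-EP Low, High | 0 | 0 | 12 − 0 = 12 |
| Visit 9 Low, High | about 6 | about 6 | 12 − 6 = about 6 |
| Visit 12 Low, High | about 9 | about 9 | 12 − 9 = about 3 |
| Non-switch Placebo | about 12 | about 12 | 0 |

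A zero appears for 3 of the 7 groups. None appears for the four switch groups.

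**12-month row, Visit 9 group.** Change from ATTeST baseline spans 6 + 12 = about 18 months, 6 of them on placebo. Change from OLE baseline spans 18 − 12 = about 6 of the 12 months on drug.

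**Visit 12 group.** Only the offsets in the table are used. The 6-monthly OLE ratings fall at about 3 + 6 = 9 and 3 + 12 = 15 months on drug. That is 9 × 365/12 = 273.75 and 15 × 365/12 = 456.25 days, on the edges of the 12-month window. Small timing shifts decide which row a rating enters, so a span for one row would be falsely precise.

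**Two ratings in one window.** Non-switch Placebo gives the cleanest check, because its clock starts at the first OLE infusion and no ATTeST spacing has to be assumed. SAP Table 2 schedules Visit x at day 28(x − 1), so Month 6 (Visit 7) is day 168. The permitted spacing is 21 to 38 days. At constant spacing:
- 21 days: Month 6 = 6 × 21 = 126 and Month 12 = 12 × 21 = 252, both in [91, 273].
- 22 days: 132 and 264, both in [91, 273]. The limit for this pair is 273/12 = 22.75 days.
- 24 days: Month 12 = 288 and Month 18 = 18 × 24 = 432, both in [274, 456].
- 28 days: 168, 336, 504 and 672, one in each printed window.

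A second route is early discontinuation. The protocol says: "All final Month 12 (Visit 13) evaluations should be performed at the time of discontinuation". At 28-day OLE spacing, a Non-switch Placebo patient evaluated at Month 8 (8 × 28 = 224) has a second rating in [91, 273] beside day 168.

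**The case against.** The strongest reply is that a third anchor is an extra quantity, not a correction. Protocol 16.2.6 asks for change from the ATTeST baseline, comparing continuous EDS-EP with patients who had differing lengths of placebo, so placebo time is meant to be inside that change. This stands. A reader might infer that the ATTeST column is biased or mistaken, and the documents do not support that. It answers the protocol's question, but not the one the row labels of the interval tables pose.

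The plan also shows the seven groups separately and summarizes the scores as well as the changes. That helps, because the offset is roughly constant within a group and its label reveals it. It does not supply the missing value: the planned baselines are ATTeST and OLE-IEDAT, so a pre-switch score is not among them.

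A reader might also count infusions as months and conclude that a Visit 12 rating on day 15 × 28 = 420 is 15 months on drug in a 12-month row. Day 420 is 420/(365/12) = about 13.8 calendar months. The count also applies 28-day spacing to ATTeST, for which the documents say only once per month.

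On duplicate ratings, the discontinuation route rests on one protocol sentence. Elsewhere, discontinuing patients are asked back for the Safety Follow-up Visit, whose schedule has no ICARS. SAP Table 2 has no early-termination visit, and unscheduled data go to listings. Nor should a reader infer that duplicates are routine on the nominal schedule: at 28 days, the check above finds none in the printed windows. The gap in the rule remains, because shorter permitted spacings produce duplicates without any discontinuation.

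**Conclusion.** The point holds for four of the seven displayed groups. In all 12 interval tables, their change columns either include about 6 (Visit 9) or 9 (Visit 12) placebo months, or omit about the first 6 or 3 months on drug. The missing selection rule is real but secondary.

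The effect is on interpretation and reproducibility. The analysis is descriptive, without hypothesis tests, so no error rate or power is involved. The efficacy objective is secondary in the SAP and exploratory in the protocol. No size in mICARS points can be given, because the documents state no progression rate.

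The figures assume nominal timing for patients who completed ATTeST. Patients discontinued during COVID-19, and those with a gap of more than 76 days between the studies, will differ. The table shells and ADaM specifications are separate documents and were not available; a selection rule may already exist there. This should be fixed, and the change is small.

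**What to change.** In SAP 7.1, add: *Active-treatment baseline = last non-missing score on or before the Date of First Infusion of Active Treatment.* Add change from it as a further column in Tables 14.2-1.7 to 1.12 and 14.2-2.7 to 2.12, and keep the ATTeST and OLE-IEDAT columns.

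Also in SAP 7.1, add: *One rating per patient per window: the one closest to the target day (182.5 × interval number); if tied, the later one.* For days 126 and 252, the distances from 182.5 are 56.5 and 69.5, so day 126 is used. If the ADaM specification already holds such a rule, a cross-reference is enough. State there whether ratings brought forward at discontinuation are eligible.

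The cost is one derived baseline, one column in 12 tables and one rule. The sponsor must supply pre-switch ATTeST scores, since SAP 5.1 names only treatment subgroups and ATTeST baseline values. Protocol 7.1.3.4 documents an endpoint assessment at ATTeST Visit 9, so this looks feasible for the Visit 9 groups. Whether ICARS was rated at ATTeST Visit 12 is not stated. If it was not, footnote that about 3 placebo months (from month 6 to month 9) remain in the Visit 12 groups' change. The new column repeats an existing one for the other three groups. The visit-based tables and the figures need no change.
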